We selected a manualized version of the NIAAA Project COMBINE alcohol counseling, "Medical Management" (MM)²⁷. This intervention helps increase problem recognition, enhance motivation, and facilitate engagement in alcohol treatment. Participants will receive weekly MM sessions for a total of 120-240 minutes consisting of 8 weekly individual sessions lasting 15-30 minutes each. The goal of MM is to help patients maintain adherence with the medication regimen using strategies that can be delivered by a typical health care provider. MM approximates a primary care approach to alcohol dependence and supports the use of pharmacotherapy. During the initial visit, the clinician reviews the patient's assessments, highlighting symptoms of alcohol use disorder and the need for treatment. The patient is advised to stop drinking. educated about unhealthy alcohol use, provided a rationale for taking the study compound, and instructed on the importance of daily medication adherence. The clinician and participant also jointly develop an individualized medication-adherence plan; the patient is encouraged to attend support groups and is given information on the medications. At follow-up visits, drinking behavior and medication adherence are ascertained, and plans for reducing drinking or achieving abstinence are revised as needed. In each session, the MM administrator will communicate and discuss medication effects, participants' concerns about any side effects and compliance barriers with the participant in understandable terms. Training will be provided to the research MD, RN and psychologist who will be MM administrators. The PI and his appointees will monitor MM

Veterans Alcohol TBI

sessions and provide training and guidance to the MM administrators as needed.

D.3.i. Measures and Schedule of Data Collection Overview

All alcohol, substance use, psychiatric, and medical measures are validated and reliable, and are only briefly outlined below due to space limits. Efforts to reduce missing data will include use of: (a) collateral informants to assist in locating participants; (b) telephone contact for missing participants; (c) flexible time periods for the completion of assessments.

Measures of Health/Biological Safety

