Baseline blood draw (genetics). Urine pregnancy at baseline, Wks 4 & 8. A participant who becomes pregnant during participation in the study will be withdrawn. Vital signs, weight, concomitant medications, suicide risk assessment¹³³, adverse events (AEs), and alcohol withdrawal (Clinical Institute Withdrawal Assessment for Alcohol, DSM-IV Version (CIWA-AD)¹³⁴ will be monitored weekly.

Alcohol and Substance Use Measures

Time-Line Follow-Back (TLFB)^{135,136} for alcohol and drug use covering the 90 days prior to entry, then at Wks 1-8, and 12. TLFB will be used to calculate the primary outcome measure, PHDD, and exploratory alcohol measures of percent drinking days, drinks per drinking day, etc. Standard drink conversions will be used for participant reports of alcohol consumption⁸. Cigarette and other substance use will also be collected by TLFB¹³⁷. The Intoximeters Alco-Sensor IV instrument will be used for *Breath alcohol concentration (BrAC)*¹³⁸ at each weekly visit. The following measures will be at baseline, Wks 4, 8 and 12: *Obsessive Compulsive Drinking Scale (OCDS)*¹³⁹ as an exploratory measure, assesses thoughts and compulsions associated with alcohol craving; *Urine Drug Screen* for opioids, cocaine, cannabis, and methamphetamine at baseline; *Ethyl Glucuronide (EtG)*, a direct metabolite of ethanol¹⁴⁰ used to provide an exploratory objective biological measure alcohol use within the last 80 hours; *Gamma Glutamyl Transpeptidase (GGT)*, a marker for alcohol consumption¹⁴¹, will provide a biological measure of heavy alcohol use.

Traumatic Brain Injury Symptoms

Neurobehavioral Symptoms Inventory (NSI)^{13,14}, a measure of postconcussive symptom severity at baseline, Wks 4, 8 and 12.

Psychiatric Diagnosis/Psychological Measures Baseline:

 Structured Clinical Interview for DSM-IV, (SCID-I/P)¹⁴²: Alcohol and other substance use diagnoses will be established using the Substance Use Disorders (SUDs) module of the SCID I/P¹⁴³. The SCID-I/P is the standard SCID-I designed for research participants identified as psychiatric patients.

The following measures will be at baseline, Wks 4, 8 and 12:

- The PTSD Checklist (PCL)¹⁴⁵, a self-report measure PTSD symptom severity over the prior 30 days
- Beck Depression Inventory¹⁴⁶: provides a measurement of depression severity¹⁴⁷

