Efforts will be made toward reducing the amount of missing data by: (a) use of a collateral informant to assist in locating patients; (b) telephone follow-up to make contact with missing patients; (c) establishment of flexible, but acceptable, time periods for the completion of each assessment; and (d) some self-report and interview measures may be administered by telephone to collect missing data from patients unwilling or unable to visit research sites to participate in a scheduled assessment session. All phone visits will include a Medical Management counseling session, during which a trained psychologist or psychiatrist (the Medical Manager) will assess adverse effects, concomitant medications, suicidality and general well-being. During phone visits, study coordinators will skip the question on the Adverse Event checklist, "Have you had suicidal thoughts or actions since the last study visit". Instead, the Medical Manager will ask that question and report back to coordinator after the Medical Management counseling session. If a Medical Management counseling session becomes logistically impossible, the PI will file a protocol violation.

Establishment of flexible, but acceptable time frames for completion of research assessments: All research assessments should be completed within an established window. Assessments scheduled for weeks 1, 2,3,5, 6, and 7 will have a window of ± 3 days for completion. Assessments scheduled for weeks 4, 8, and 12, have a window of ± 1 week for completion. This flexibility will enhance the ability of staff to schedule patients for assessments as close as possible to the protocol defined period. Patients likely to miss appointments should be scheduled early in the window to allow for successive attempts to complete ratings within the desired time frame.

After receiving CHR and R&D approval, we will be converting most of our questionnaire measures to a digital format, so that this questionnaire data can be collected and managed using the San Francisco VA Medical Center's Stress and Health Research Program Data Management Research Database System.

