PI: [name] This form is to be administered upon completion of the study (as defined by attending Week 12 visit) or at termination to document the last day of study medication ingestion, number of visits attended and/or reasons for terminating.

D.4.b.7. PARTICIPANT - END-OF-STUDY QUESTIONNAIRE

This measure is administered at Week 12 to assess the participant's opinion of participation and what was helpful/useful during treatment.

D.4.c. Measures of Health/Biological Safety

D.4.c.1. OVERVIEW OF HEALTH/BIOLOGICAL SAFETY MEAUSURES

Safety evaluations will include: entry medical history and physical examination, weekly vital signs monitoring, weekly breath alcohol concentration (BrAC), weekly CIWA-AD (clinical alcohol withdrawal assessment), weekly monitoring for adverse events, suicide risk assessment at baseline, periodic clinical laboratory tests (complete labs including urinalysis at baseline, periodic renal function and liver function tests, and urine pregnancy tests performed every 28 days on women of childbearing potential.

D.4.c.2. MEDICAL HISTORY AND PHYSICAL EXAMINATION

A medical history and physical examination will be completed at baseline during the screening period. Study physicians will screen medical records. This information will be recorded on the physical examination form.

D.4.c.3. CLINICAL LABORATORY TESTS FOR HEALTH AND SAFETY MONITORING

The following tests will be performed by the San Francisco VAMC clinical laboratory.

Clinical laboratory tests at baseline (Screening phase):

Blood samples will be collected for serum chemistry, liver panel (LFTs), renal panel and complete blood count (CBC) and a urine sample will be collected for urinalysis, and, for women – urine pregnancy test.

If AST or ALT are >5 times the upper limit of the normal range, or if serum bilirubin is >2 times the upper limit of normal, these tests will be repeated, and if the repeat tests still exceed these limits, the participant will be excluded.

Clinical laboratory tests for health and safety monitoring throughout the study: Renal and hepatic panels will be repeated at Visits 4 and 8 for all participants.

D.4.c.4. BIRTH CONTROL/PREGNANCY ASSESSMENT

Birth Control/ Pregnancy Assessment will be done at baseline/screening at weeks 4, 8, and 12. Any participant who becomes pregnant during participation in the study will be withdrawn. The results will be recorded on a Birth Control/pregnancy Assessment Form.

D.4.c.5. VITAL SIGNS

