PRESCREENING **CPRS** Prescreen Phone Prescreen CONSENT Informed Consent HIPAA Research Subject's Bill of Rights Patient Locator SCREENING PHASE – BASELINE MEASURES + PROCEDURES The following baseline measures and procedures will occur during approximately 3 visits over roughly 1 week and take approximately 4.5 to 7 hours to complete. Measures **Eligibility Form** Review of Medical History **TLFB** - Timeline Followback **Concurrent Medications Form Concurrent Treatments Form** AE Spontaneous Form AE Checklist Form SCID – Structured Clinical Interview for DSM-5 (Patient Edition) Demographics TBI Evaluation CIWA - Clinical Institute Withdrawal Assessment for Alcohol, DSM-IV Version (CIWA-AD) Suicide Risk Assessment NSI – Neurobehavioral Symptom Inventory AUDIT – Alcohol Use Disorders Identification Test SIP-2R – Short Index of Problems OCDS - Obsessive Compulsive Drinking Scales PACS – Penn Alcohol Craving Scale FTQ – Family Tree Questionnaire TAA – Thoughts About Abstinence RTC - Readiness to Change Ruler SHAS – Subjective High Assessment Scale EVAR-B – Evaluation of Risks Scale PCL – PTSD Checklist POMS – Profile of Mood States BDI-II – Beck Depression Inventory BAI – Beck Anxiety Inventory BIS-11 – Barratt Impulsivity Scale PSQI – Pittsburgh Sleep Quality Index ISI – Insomnia Severity Index DERS – Difficulties in Emotion Regulation Scale DTS – Distress Tolerance Scale APT – Alcohol Purchase Task

Veterans Alcohol TBI

	FI. [name]
TMT A + B – Trail Making Test A & B	
WAIS 4 – Arithmetic	
WAIS 4 – Digit Span	
Stroop Inhibition	
COWA – Controlled Oral Word Association	
BART – Balloon Analogue Risk Task	
IGT – Iowa Gambling Task	
SST – Stop Signal Task	
AAT – Alcohol Approach Task	
Medication Dispensing Form	
Procedures	
Breath Alcohol Concentration (BrAC)	
Physical Exam	
Clinical Labs – renal panel, hepatic panel and GGT	
Ethyl Glucuronide (EtG)	
Urine Drug Screen	
Blood draw for genetics (optional)	
Vitals (Blood pressure, heart rate, temperature)	
Weight	
Medical Management	
Assess birth control method and perform urine pregnancy test (women only)	
Review Medical Event Monitoring System (MEMS)	
Drug Accountability	
Dispense Medication	

Following completion of Screening Phase: Lab Manager will review inclusion/exclusion criteria. If eligible, the participant will proceed to the Treatment Phase.

Randomization assignment occurs at the end of Screening Phase.

D.5.b. Treatment Phase

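### At phone visits the coordinator skips the suicidality item; if the Medical Management session cannot be held, the plan states only a protocol-violation report, so read literally nobody asks it

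*Combined protocol and SAP*

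**What the plan says.** Section D.4.a, in its paragraph on reducing missing data, allows phone visits and requires each to include an MM session in which a psychologist or psychiatrist, the Medical Manager, covers suicidality among other things. It then sets out a hand-over in three steps.

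- "During phone visits, study coordinators will skip the question on the Adverse Event checklist", the question being the one on suicidal thinking or behaviour since the previous visit. No exception is given.
- The substitute is named next: "Instead, the Medical Manager will ask that question and report back to coordinator after the Medical Management counseling session". This is the only reassignment of the item.
- For a session that fails, the whole of the stated response is this: "If a Medical Management counseling session becomes logistically impossible, the PI will file a protocol violation".

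The next paragraph of D.4.a sets completion windows of ±3 days for weeks 1, 2, 3, 5, 6 and 7 and ±1 week for weeks 4, 8 and 12. It adds that participants likely to miss visits "should be scheduled early in the window to allow for successive attempts to complete ratings".

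Other sections bear on the point. D.4.c.8 has an open-ended adverse-event question (item a) and an adverse-event checklist (item b), both weekly. D.3.i lists "Vital signs, weight, concomitant medications, suicide risk" assessment among items monitored weekly, whereas D.4.c.1 has "suicide risk assessment at baseline, periodic clinical laboratory tests". The screening list in D.5.a contains "Suicide Risk Assessment"; the treatment and follow-up lists in D.5.b and D.5.c do not. E.1 and E.1.c.1 make the PI responsible for watching for new adverse events at visits and telephone contacts. D.3.h says of MM staffing: "Training will be provided to the research MD, RN and psychologist who will be MM administrators".

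**The concern.** Giving this question to a clinician on the phone is sensible. The difficulty is what follows when the clinician's session fails. The third step removes the only person assigned in the second, while the first stays in force. A coordinator who follows the text exactly has reached the participant and does not ask.

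Section B.4 links suicide risk to both TBI and heavy drinking. Section D.2.c excludes a suicide attempt in the past 3 months, ideation with intent in the past 30 days, and psychiatric disorders judged unstable; ideation without intent is not in itself an exclusion. Phone contact is meant for people unwilling or unable to attend, so the gap falls where nobody sees the participant face to face. Usual care continues (B.1), and staff may contact the clinical team after several missed appointments (E.1.a.4), but neither replaces asking someone who has just been reached.

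**Working it through.** This is mainly a matter of setting the sections side by side; only the length of a possible delay involves arithmetic.

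**1. Follow the written steps for a phone visit without an MM session (D.4.a).** The coordinator skips the item. The Medical Manager, who should ask it, has no session in which to do so. The PI files a violation. No sentence returns the item to the coordinator, names another clinician, or requires a call-back. The section does not say whether MM takes place on the coordinator's call or separately, and nothing here depends on that.

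**2. Test each provision that might restore the question.**

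| Provision | What it gives | Does it clearly restore the item? |
|---|---|---|
| D.4.c.8 item b | Checklist asked weekly | No. It is a general duty, and D.4.a specifically takes this item out of the coordinator's checklist at phone visits. It can still be read as keeping the duty that someone ask. |
| D.4.c.8 item a | Open-ended question weekly | No. It does not ask about suicidality. |
| D.3.i | Suicide risk assessment weekly | Not reliably. D.4.c.1 places it at baseline, and D.3.i gives no phone procedure or assessor. |
| E.1, E.1.c.1 | PI watches for adverse events at telephone contacts | No. It does not put the question to the participant. |
| D.4.a windows | Room for another attempt | Permitted, not required. |

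The silence of the D.5 visit lists is weak evidence on its own. The list for weeks 4 and 8, for example, omits the PTSD Checklist that D.4.f.1 schedules then. The reason for not relying on D.3.i is its tension with D.4.c.1.

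**3. Length of the delay for one such contact.** Inputs: nine visits, weeks 1-8 and 12 (D.3.k); windows from D.4.a; nominal visit day = 7 × week; the failed call falls on the nominal day.

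- Session retried inside the window: 0-3 days (weeks 1, 2, 3, 5, 6, 7) or 0-7 days (weeks 4, 8, 12).
- No retry, weeks 1-7 (7 of 9 visits): 7 × (w + 1) − 7 × w = 7 days.
- No retry, week 8 (1 of 9): 84 − 56 = 28 days. D.5.b also lists visits at weeks 9-11; if week 9 is held, 63 − 56 = 7 days.
- No retry, week 12 (1 of 9): no later visit is scheduled.

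The item looks back to the previous study visit. If a phone visit counts as one, which the plan does not say, the next asking would not literally cover the period before the failed contact.

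**4. Frequency.** The documents give neither the number of phone visits nor how often MM fails, so no rate is computed.

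**The case against.** The best reply is that D.4.a changes who asks, not whether the question is asked. The suicidality question sits on the checklist that D.4.c.8 item b requires weekly, and the skip is followed at once by its substitute, so it can be read as depending on that substitute. This reading is available. It does not settle the matter, because D.4.a is the more specific rule, has no exception, and provides for the failed session without mentioning the question.

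Further points are fair. Because the PI files the violation, the PI learns of the failure; but no call to the participant is required. D.4.c.1 does not say the suicide risk assessment is done only at baseline, so D.3.i could coexist with it; but D.3.i still names no assessor or phone procedure. The windows make rescheduling the natural course before a session is declared impossible, and good staff would probably do so; that makes the gap smaller but leaves it to initiative. The depression inventory is due at weeks 4, 8 and 12, and D.4.a lets some self-report measures be given by phone; it does not say which, and this would not cover the other weeks.

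Two points stand in full. The event needs a phone visit in place of an attended one and then a failed session, in a trial of 30, so it is probably uncommon. And a coordinator who elicits suicidal ideation with no clinician available needs a defined next step, so a remedy that only tells the coordinator to ask and notify the PI would be inadequate.

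**Conclusion.** The concern holds as a gap in a safety procedure. The plan foresees the failed session, and the rule it states for that event, followed exactly, leaves the suicidality item unasked at that contact. The delay for one such contact is 0-7 days with a retry in the window. Without one it is nominally 7 days for most visits and up to 28 after week 8, with no scheduled contact after week 12. These figures assume calls on nominal days and the schedules cited above.

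A reader might infer more than the documents support:

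- That suicidality goes unmonitored at phone visits in general. It does not; the Medical Manager asks whenever the session is held.
- That the plan releases everyone from asking. It does not say so, and D.4.c.8 item b leaves room for a duty to ask; the fault is that the duty is not clearly assigned.
- That 28 days is the expected delay. It applies to one visit of nine, and only if nothing is retried and the week 9 visit is not held.
- That the results are affected. Nothing here touches the primary analysis, alpha or power.

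It merits correction before further phone visits because the possible harm is serious and the remedy cheap, not because the event is shown to be frequent.

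**What to change.** In D.4.a, replace the unconditional skip with a conditional one:

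1. The coordinator skips the item only if the Medical Manager holds the session for that contact and records the answer.
2. If the session cannot be held, the PI, the study physician or another MM-trained clinician (D.3.h provides for an MD, an RN and a psychologist) phones the participant the same day and asks the item. The protocol-violation report is filed as well.
3. If no clinician can make that call, the coordinator asks the existing checklist item. On a positive answer the coordinator follows a pre-specified urgent step that does not depend on those clinicians being free, such as keeping the participant on the line and transferring to on-call or emergency psychiatric services or a crisis line. The PI or study physician is notified as soon as one can be reached.

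Apply this to every phone contact, including week 12. Whether MM is held at week 12 at all is a separate inconsistency (D.4.a against D.3.h and D.5.c) that this change does not resolve.

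The cost is a short paragraph, same-day clinician cover and an agreed urgent pathway; no new instrument is needed. The drawback is that a non-clinician may occasionally ask the item first.
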